9.5.3 Treatment and Follow-up Procedures (Cycles 1 and 2)

The following text represents Cycles 1 and 2 assessments and procedures unless otherwise specified (PK and ECG assessments are done only in Cycle 1). Refer to [Table 16](#).

9.5.3.1 Day 1 (Before Dosing)

- Complete physical examination (not required if done ≤ 4 days before Day 1).
- Vital signs.
- ECOG performance status.
- Triplicate 12-lead ECG (rhythm, atrial rate, ventricular rate, PR interval, QRS duration, and QT/QTc, morphology and overall interpretation).
- Health-related QOL by EQ-5D 5 level (EQ-5D-5L) ([Appendix 4](#)).
- Weight and BSA calculation (use height from screening; BSA recalculation if weight changes $\pm 10\%$ or more from screening).
- All study-procedure-related AEs and concomitant medications.
- Sample collection for laboratory assessments, including:
 - Hematology (see [Table 17](#)) (not required if done ≤ 4 days before Day 1).
 - Serum chemistry (see [Table 17](#)) (not required if done ≤ 4 days before Day 1).
 - Serum or urine pregnancy test (Cycle 2 only): for women of child-bearing potential only.

- Hospital admission and discharge dates (and the main reason for hospitalization), as well as all blood and platelet transfusions (blood product transfused and units), since the last visit.

9.5.3.2 Day 1 (During and After Dosing)

- 12-lead ECG (triplicate) in Cycle 1 only: at 1-2 hours postdose.
- At selected centers: sample collection for PK in Cycle 1 only: Refer to Section 9.3 for details about sampling.
 - For assigned subjects receiving SGI-110: postdose at 1.5 hours (± 30 minutes) and 3 hours (± 1 hour), with time of sampling recorded.
 - For assigned subjects receiving decitabine IV: at 30 minutes (± 10 minutes) into the infusion, and then immediately before the end of infusion (at 1 hour)
- All treatment-emergent AEs and concomitant medications.

9.5.3.3 Dosing Days (Days 2-5, Days 2-7, or Days 2-10, Depending on Study Treatment)

- Vital signs (before dosing).
- All AEs and concomitant medications.
- Cycle 1 only: At selected centers: Day 5 sample collection for PK: Refer to Section 9.3 for details about sampling.
 - For assigned subjects receiving SGI-110: postdose at 1 hour (± 30 minutes) and 5 hours (± 2 hour), with time of sampling recorded.
 - For assigned subjects receiving decitabine IV: immediately before the end of infusion (at 1 hour); and at 5 minutes (± 2 minutes) and 3 hours (± 1 hour) after the end of infusion, with time of sampling recorded.

9.5.3.4 Days 8, 15, and 22

- All AEs and concomitant medications.
- Hematology (see Table 17).
- Hospital admission and discharge dates (and the main reason for hospitalization), as well as all blood and platelet transfusions (blood product transfused and units), since the last visit.

9.5.4 Treatment and Follow-up Procedures for Cycles ≥ 3

Table 16 shows assessments and procedures for Cycles ≥ 3 .

9.5.4.1 Day 1 (Before Dosing), Cycles ≥ 3

Day 1 for Cycles ≥ 3 has a visit window of +7 days, unless otherwise specified below.

- Complete physical examination (not required if done ≤ 4 days before Day 1).
- Vital signs.
- ECOG performance status.
- Health-related QOL EQ-5D-5L ([Appendix 4](#)).
- Weight and BSA calculation (use height from screening; BSA recalculation if weight changes $\pm 10\%$ from screening).
- All AEs and concomitant medications.
- Sample collection for laboratory assessments, within 4 days of Day 1, including:
 - Hematology (see [Table 17](#)).
 - Serum chemistry (see [Table 17](#)).
 - Serum or urine pregnancy test: for women of child-bearing potential only.
- BM aspirate/biopsy required at the end of Cycles 2, 4, and 6 (Day 1 of Cycles 3, 5, and 7, ± 7 days) unless PB shows persistence of leukemic blasts that excludes the possibility of a marrow response. After BM assessment at the end of Cycle 6 (Day 1 of Cycle 7), repeat BM aspirate/biopsy every 3 months for the first year on study and then every 6 months thereafter until PB or BM assessment shows disease progression or relapse. (See [Section 9.2](#).)
- Hospital admission and discharge dates (and the main reason for hospitalization), as well as all blood and platelet transfusions (blood product transfused and units), since the last visit.

9.5.4.2 Dosing Days (Days 2-5, Days 2-7, or Days 2-10, Depending on Study Treatment), Cycles ≥ 3

- Vital signs (before dosing).
- All AEs and concomitant medications.

9.5.4.3 Day 15 (Cycles ≥ 3)

- All AEs and concomitant medications.
- Hematology (see [Table 17](#)).
- Hospital admission and discharge dates (and the main reason for hospitalization), as well as all blood and platelet transfusions (blood product transfused and units), since the last visit.

9.5.5 Treatment Discontinuation and Safety Follow-up Visit

Each subject should be followed up, to document the occurrence of any new AEs, for at least 30 (+7) days after his or her last dose of study treatment, or until any AE or SAE assessed as related to study treatment or procedures has resolved to a clinically acceptable or stable resolution (see Section 10.4). Subjects who withdraw consent should still be encouraged to complete this visit. The following evaluations are to be performed:

- Complete physical examination.
- Vital signs.
- ECOG performance status.
- 12-lead ECG (triplicate).
- Health-related QOL EQ-5D-5L (Appendix 4).
- All AEs and concomitant medications.
- Sample collection for clinical laboratory tests, including:
 - Hematology (see Table 17).
 - Serum chemistry (see Table 17).
- Serum or urine pregnancy test: for women of child-bearing potential only.
- Hospital admission and discharge dates (and the main reason for hospitalization), as well as all blood and platelet transfusions (blood product transfused and units), since the last visit.
- Subsequent anti-leukemia therapy (regimen and start date).
- Disease progression status (subjects who discontinue treatment before documented disease progression must undergo PB and BM aspirate/biopsy assessments until disease progression or relapse is confirmed).

The treatment discontinuation and safety follow-up visit may be conducted by telephone if needed to collect, at minimum, AE information.

9.5.6 Long-term Follow-Up

Long-term follow-up starts after subjects discontinue study treatment. Long-term follow-up visits will be either monthly or every 3 months, depending on when the subject discontinues study treatment:

- For subjects who discontinue treatment before Cycle 6, initial follow-up visits will be conducted monthly (± 7 days) until 6 months after the start of study treatment, and then visits will be conducted every 3 months (± 2 weeks), until death.
- For subjects who discontinue treatment after Cycle 6, long-term follow-up visits are required every 3 months (± 2 weeks), until death.

Monthly long-term follow-up procedures (for subjects who discontinue treatment before Cycle 6):

- Health-related QOL EQ-5D-5L ([Appendix 4](#)).
- Hospital admission and discharge dates (and the main reason for hospitalization), as well as all blood and platelet transfusions (blood product transfused and units), since the last visit.
- Subsequent anti-leukemia therapy (regimen and start date).
- For subjects with no documented disease progression on treatment:
 - Hematology and/or BM aspirate/biopsy (≥ 1 year after the start of study treatment, BM aspirate/biopsy every 6 months) until disease progression or relapse is documented.
 - Disease progression status.
- Survival follow-up.

Long-term follow-up procedures for visits every 3 months (± 2 weeks) (for subjects who discontinue treatment after Cycle 6 and for subjects have completed the monthly long-term follow-up visits described above):

- Subsequent anti-leukemia therapy (regimen and start date).
- For subjects with no documented disease progression:
 - Hematology and/or BM aspirate/biopsy (≥ 1 year after the start of study treatment, BM aspirate/biopsy every 6 months).
 - Disease progression status.
- Survival follow-up.

Long-term follow-up visits may be conducted by telephone if needed.

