9.2 Efficacy

PB will be assessed at screening and on Day 1 of each cycle for response evaluation. BM aspirate or biopsy will be performed at screening then at the end of Cycles 2, 4, and 6 (Day 1 of Cycles 3, 5, and 7) unless PB shows persistence of leukemic blasts that excludes the possibility of a marrow response. After Cycle 6 BM assessment (Day 1 of Cycle 7), BM aspirate/biopsy will be repeated every 3 months for the first year on study and then every 6 months thereafter until PB or BM assessment shows disease progression or relapse.

CR will be assessed by modified IWG 2003 AML Response Criteria (see Section 11.6), based on blood sampling and BM aspirate/biopsy. Response assessment will be based on BM blinded review and the most concomitant PB counts. After blinded BM response is confirmed, assessment of normal count recovery will be done based initially on the most concomitant PB counts and in later cycles on PB counts from Day 1 of each cycle to avoid transient treatment-induced normal count suppression. The central pathologist who evaluates BM and PB counts for response assessment, as well as the central response reviewer, will be blinded to treatment assignment (Section 6.2).

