- j. **Concomitant medications:** Document all concomitant medications within 14 days before randomization to 30 days after the last dose of study treatment.
- k. **Hematology:** Include complete blood count with manual differential. Day 1 hematology for all cycles does not need to be repeated if done within 4 days of Day 1. For Cycles >6, hematology will be required only on Day 1. Additional hematology assessment may be done for safety or for subject management at the investigator's discretion. Collection, analysis, and reporting information are described in the Study Lab Manual.
- l. **Serum chemistry:** Refer to Table 17. Day 1 chemistry for all cycles does not need to be repeated if done within 4 days of Day 1. Additional chemistry assessment may be done for safety or for subject management at the investigator's discretion. Collection, analysis, and reporting information are described in the Study Lab Manual.
- m. **Pregnancy test:** Women of child-bearing potential only. The screening test must be done within 7 days of Cycle 1 Day 1 (ie, Day -7 to -1); test not required on Cycle 1 Day 1 if done at screening.
- n. **PK:** At selected study centers: Subjects receiving SGI-110 and subjects in the TC group who receive decitabine IV in Cycle 1 only. Refer to Section 9.3 for details.
- o. **Molecular genetics and cytogenetics:** BM and blood samples will be collected within 28 days before starting study treatment to evaluate cytogenetics (chromosome abnormalities) and gene mutations (such as FLT3-ITD, NPM1, CEBPA).
- p. **BM aspirate or biopsy:** BM aspirate and/or biopsy differential count will be performed according to local standard practice. The screening aspirate must be collected within 28 days before starting study treatment. If BM aspirate/biopsy was completed before consent for this study, center must be able to obtain slides for central reader and samples for screening cytogenetic assessments. A biopsy should be done if no spicules are observed in the aspirate. Marrow aspirate or biopsy differential may include the following:
- Total cells counted
 - Blasts
 - Promyelocytes
 - Myelocytes
 - Metamyelocytes
 - Segmented neutrophils
 - Eosinophils
 - Basophils
 - Lymphocytes
 - Plasma cells
 - Monocytes
 - Pronormoblasts
 - Normoblasts
 - M:E ratio
 - Auer rods
 - Megakaryocytes: increased, normal, decreased, absent
 - Presence of dysplasia: dysE, dysG, dysM
 - Cellularity: % cellularity: hypocellular, hypercellular, normocellular
 - Other

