11.6.6 Progression-free Survival (PFS)

Progression is defined as the earliest occurrence of one of the following:

- For subjects with CR, CRi, or CRp, the confirmed (at least 2 PB samples at least 1 week apart) appearance of leukemic blasts in PB by investigator or central assessment, OR $\geq 5\%$ leukemic blasts in the BM by blinded central pathologist assessment.
- For all other subjects, when PB or BM shows evidence of continued increase in blasts % that necessitates alternative therapy.
- Death.

PFS is defined as the number of days from randomization to the earliest date of investigator's assessment of disease progression or relapse by PB assessment or blinded BM assessment, whichever occurs first, or death (regardless of cause). PFS time will be censored on the last date the subject is known to be alive without a relapse/disease progression. Subjects receiving other anti-leukemia therapy before occurrence of a relapse/ disease progression will also be censored at the date of the start of other anti-leukemia therapy.

PFS will be compared between the 2 treatment groups using a stratified log-rank test at an alpha level of 0.05, or 0.01, as appropriate, if CRc and NDAOH test results are significant at that required level. The medians and quartiles of PFS will be summarized.

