### 7.3.6 Progression-free Survival

Progression is defined as the earliest occurrence of one of the following:

- For subjects with CR, CRi, or CRp, the confirmed (at least 2 PB samples at least 1 week apart) appearance of leukemic blasts in PB by investigator or central assessment, OR  $\geq 5\%$  leukemic blasts in the BM by blinded central pathologist assessment.
- For all other subjects, when PB or BM shows evidence of continued increase in blasts % that necessitates alternative therapy.
- Death.

PFS is defined as the number of days from randomization to the earliest date of investigator's assessment of disease progression, subject receives an alternative anti-leukemia therapy, or relapse by PB assessment or blinded BM assessment, whichever occurs first, or death (regardless of cause). PFS time will be censored on the last date the subject is known to be alive without a relapse/disease progression.

$$\text{PFS in days} = (\text{earliest date of progression, relapse, alternative anti-leukemia therapy, death or censoring} - \text{date of randomization})$$

PFS will be compared between the 2 treatment groups using a stratified log-rank test (by the same stratification factors as used at randomization) at an alpha level of 0.05, or 0.01, as appropriate, if CRc and NDAOH test results are significant at that required level (see

[figure not shown]
Section 7.3.7). The median (and quartiles) duration of PFS and the associated 95% CI for each treatment arm will be estimated using the Kaplan-Meier method. In addition, the HR and its 95% CI will be estimated using a Cox proportional-hazard model with treatment group as the independent variable and stratified by the same randomization stratification factors as used for the log-rank test. In a supportive analysis, the assumption of proportional hazards will be evaluated to assist interpretation of the Cox regression analysis results.

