### 7.3.10 Duration of Complete Response

Duration of CR (in number of days) will be calculated from the first time a CR is observed to time of relapse (defined as the earliest time point whereby BM assessment or PB assessment indicate relapse/disease progression due to reappearance of leukemic blasts in PB or  $\geq 5\%$  leukemic blasts in BM; see Section 7.3.6). The duration of CR will be censored at the last available time point at which a relapse/disease progression was not observed. Duration of CR will be estimated using a Kaplan-Meier method for subjects who achieved a CR during the study.

The median and quartiles of duration of complete response, as well as their respective 95% CIs will be provided.

To take all subjects in the Efficacy Analysis Set into consideration when analyzing duration of CR, a separate Kaplan-Meier analysis including all subjects will be conducted with a 0-day event duration assigned to subjects who did not achieve a CR. The median and quartiles of duration of complete response, as well as their respective 95% CIs will be provided.

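### A single blast-positive blood sample followed by death or new therapy is censored in duration of CR, because the two-sample relapse rule has no provision for a missing second sample

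*Protocol*

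**What the plan says.** **Relapse rule.** For subjects with CR, CRi or CRp, protocol 11.6.6 gives two routes to relapse, joined by OR. The blood route is "the confirmed (at least 2 PB samples at least 1 week apart) appearance of leukemic blasts in PB by investigator or central assessment". The marrow route is 5% or more "leukemic blasts in the BM by blinded central pathologist assessment", and it needs no confirmation. SAP 7.3.6 repeats the blood rule: "the confirmed (at least 2 PB samples at least 1 week apart) appearance of leukemic blasts in PB".

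**Duration of CR.** Protocol 11.6.10 and SAP 7.3.10 run duration from first CR to the earliest time point at which marrow or blood indicates relapse, and refer back to the PFS section for the definition. On censoring, SAP 7.3.10 says: "The duration of CR will be censored at the last available time point at which a relapse/disease progression was not observed". Death is not listed as an event.

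**Blood schedule.** On treatment, Table 16 footnote k states: "For Cycles >6, hematology will be required only on Day 1". Off treatment, for subjects who stop after Cycle 6, protocol 9.5.6 states that "long-term follow-up visits are required every 3 months", plus or minus 2 weeks. Subjects who stop before Cycle 6 are seen monthly until 6 months after starting treatment, then 3-monthly. Follow-up visits may be by telephone.

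**Marrow schedule.** Protocol 9.2: "BM aspirate/biopsy will be repeated every 3 months for the first year on study and then every 6 months thereafter", continuing "until PB or BM assessment shows disease progression or relapse". Section 9.5.6 is looser and accepts hematology and/or marrow at follow-up visits. Footnote r and section 9.5.5 continue blood and marrow assessment until relapse is confirmed.

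**Extra samples.** Section 9.6 allows unscheduled blood and marrow at the investigator's discretion.

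**The concern.** The blood rule needs a second sample that the visible schedule does not call for. Neither document says what happens when one positive sample is followed by death or new anti-leukemia therapy. If the two-sample rule carries over to duration of CR, as the cross-reference implies, that subject has not relapsed and is censored at the last relapse-free assessment.

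The subjects lost this way are those whose disease moves fastest after relapse. Their censoring depends on the outcome being measured, so the Kaplan-Meier estimate of duration of CR is pushed upward. No formal test depends on it. However, protocol 4.2 justifies CR as a co-primary endpoint by the value of durable CR, so the duration estimate will be read alongside the CR result.

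The documents also leave open which of two positive samples dates the relapse.

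**Working it through.** The plan states no duration of CR, relapse count or confirmation rate, so there is no figure of its own to reproduce.

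**1. Can the schedule confirm a relapse?** The shortest required gaps are:
- Cycles >6: 28 days
- monthly follow-up: 30 - 14 = 16 days
- 3-monthly follow-up: 91 - 28 = 63 days

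All exceed 7 days and the rule sets no maximum gap, so two consecutive scheduled samples satisfy it. The problem arises only when the subject dies or starts new therapy before the second sample.

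**2. How likely is that, on the blood route alone?** Let m be the median time in months from relapse to death or new therapy. The documents do not give m; 2-4 months is assumed. With exponential times and 30.44 days per month, the chance that a subject with a first positive sample has died or changed therapy before the next draw, g days later, is 1 - 2^(-g / (30.44 m)).

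| m (months) | g = 28 days | g = 91 days |
|---|---|---|
| 2 | 1 - 2^(-0.460) = 27% | 1 - 2^(-1.495) = 64% |
| 3 | 1 - 2^(-0.307) = 19% | 1 - 2^(-0.996) = 50% |
| 4 | 1 - 2^(-0.230) = 15% | 1 - 2^(-0.747) = 40% |

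These are upper figures, because they allow no marrow and no unscheduled draw.

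**3. Effect on the Kaplan-Meier median.** Simulation of 60,000 responders per scenario.
- From the documents: visits every 28 or 91 days; follow-up of 12 to 33 months (12 months after a 21-month enrollment; 21 + 12 = 33).
- Assumed: exponential time to relapse with true median 6 months; m of 2-4 months; every relapse visible in blood; random visit phase; no unscheduled samples.
- Confirmed relapses are dated at the first positive sample. Subjects who die before any positive sample are censored in every version.

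| 3-monthly visits | Median duration of CR, months |
|---|---|
| Rule as written, marrow never helps | 12.7-24.8 |
| Rule as written, marrow confirms half of the relapses | 10.1-13.2 |
| Rule as written, marrow confirms all | 8.7-10.2 |
| First positive sample counts | the same as marrow confirming all, within simulation error |

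On 28-day visits with no marrow, the rule as written gives 7.9-9.8 months, against 6.9-7.4 if the first positive counts. Repeat runs of the longest 3-monthly figure gave 24 to 24.8, so its decimal is not firm.

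**4. What the rule does not explain.** Even when every first positive counts, the 3-monthly median is about 9-10 months against a true 6. That excess comes from late detection and from censoring deaths before any positive sample. Only the rise above about 9-10 months is due to the two-sample rule.

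**5. Dating.** If relapse were dated at the confirming blood sample, each blood-confirmed relapse would move later by one further interval, 28 or about 91 days.

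**The case against.** **Marrow is a real second route.** One central reading of 5% or more blasts is enough. A single positive blood sample is not relapse under the rule, so it does not stop the marrows, and footnote r and 9.5.5 continue them until relapse is confirmed. A reader of 9.2 and 9.5.6 might infer that marrow gives no back-up; the documents do not support that. If a marrow accompanies every 3-monthly visit, the two-sample rule costs nothing. The cover is partial, though: marrow falls to 6-monthly after the first year, and 9.5.6 accepts hematology alone.

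**Further samples are allowed.** Section 9.6 permits extra draws, and 9.5.1 asks for more frequent laboratory work when clinically indicated. This stands, but neither fixes a repeat draw after a first positive sample. The grid of Table 16 and its footnotes a to e were not readable in the text available, so the absence of a requirement is an absence from the visible text.

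**The sparse schedule does not apply to everyone.** Early discontinuers have monthly visits to month 6, every subject has a safety visit with hematology about 30 days after the last dose, and SGI-110 continues while the subject benefits. Protocol 9.5.4.3 also lists Day 15 hematology for Cycles 3 and above with no stop at Cycle 6, in conflict with footnote k and the synopsis.

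**The duration text may already intend the first sample.** The earliest-time-point wording favors dating at first reappearance. But its cross-reference brings in the two-sample rule, and nothing covers a lone positive sample.

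**The impact is limited.** SAP 7.3.7 treats duration of CR as supportive, without formal testing. Protocol 11.6.10 mentions a log-rank comparison in an all-subject version, but outside the alpha hierarchy. PFS is largely protected: death is an event in both documents, and the SAP also counts new therapy. CR rate and OS are untouched. All of this stands.

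**Conclusion.** The gap is real and narrow. A responder with one blast-positive blood sample, no second sample before death or new therapy, and no qualifying marrow is censored in duration of CR although relapse was seen. The direction of the bias is upward.

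The size cannot be known from the documents. It depends on time from relapse to death or new therapy, marrow use and unscheduled draws, and none of these is given. Under the stated assumptions, the 3-monthly median rises from about 9-10 months to 10.1-13.2 if marrow confirms half of the relapses. The 12.7-24.8 months applies only if marrow never helps.

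A reader might go further and infer that many relapses are never confirmed, or that the bias differs between arms. Neither is supported. The next scheduled sample qualifies, one marrow is enough alone, and extra draws are allowed. The follow-up rules are the same in both arms, and no arm difference in time on treatment while in CR is documented.

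This is a low-cost improvement to a supportive endpoint. It does not threaten the primary analyses.

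**What to change.** In SAP 7.3.6 and 7.3.10, and in protocol 11.6.6 and 11.6.10:

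1. Date blood relapse at the first blast-positive peripheral blood sample.
2. Count it as an event if a second sample or a marrow confirms it, or if death or new anti-leukemia therapy occurs before a second sample.
3. Report the confirmed-only version as a sensitivity analysis.

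Reconcile the Day 15 hematology text for Cycles 3 and above (protocol 9.5.4.3) with the synopsis and Table 16 footnote k.

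A scheduled repeat count after a first positive sample is optional; the fix does not depend on it.

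The cost is a few lines of wording and one extra table. The downside is small: a few subjects with transient regenerating blasts who then die would be counted as relapsed, and the confirmed-only analysis would show how much that matters. The fix does not remove the excess from sparse visits or from deaths before any positive sample.
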